9.1.2.2 Follow-Up Period

All subjects, regardless of whether they complete all 24 months of treatment or discontinue study drug prematurely, will complete 2 post-treatment Follow-up Visits; one 4 weeks after the last dose of study drug and a second 12 weeks after the last dose of study drug (Visit 14 and Visit 15 respectively). If clinically indicated, more frequent safety assessments can be made as UNS assessments or visits during the post-treatment Follow-up Period.

In some cases, UNS visits will be needed to follow-up on safety or other findings, and the related assessments (outlined in the Schedule of Assessments) will depend on the reason for the UNS visit, and will be decided at the discretion of the investigator.

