9.1.4 End of Study

The end of the Core Study will be the date of the last study visit (Visit 15) for the last subject in the double-blind Randomization Phase. The end of the Extension Phase will be the date of the last study visit for the last subject enrolled in the Extension Phase. (revised per Amendments 03 and 06)

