9.7.1.1.2 SECONDARY ENDPOINTS

The key secondary endpoints of the study are as follows (revised per Amendment 06):

- Change from baseline in ADCOMS at 24 months in the combined studies
- Change from baseline in amyloid PET SUVR at 24 months for brain amyloid levels in the combined studies
- Change from baseline in amyloid PET SUVR at 24 months for brain amyloid levels in the individual studies

The other secondary endpoints of the study are as follows (revised per Amendment 06):

- Change from baseline in the CDR-SB at 24 months for subjects enriched by baseline PET SUVR, eg, between 1.2 and 1.6, in the combined studies
- Change from baseline in the ADCOMS at 24 months for subjects enriched by baseline PET SUVR, eg, between 1.2 and 1.6, in the combined studies
- The rate of change over time (mean slope) based on CDR-SB score over 24 months in the combined studies
- Time to worsening of CDR scores by 24 months (eg, the worsening of global CDR score is defined as an increase from baseline by at least 0.5 points on the global CDR scale on 2 consecutive scheduled visits at which global CDR is undertaken) in the combined studies
- Time to conversion to dementia by 24 months for subjects who were not clinically staged as dementia at Baseline based on clinical diagnosis in the combined studies (revised per Amendment 01)
- Change from baseline in CDR-SB at 27 months (ie, 24 months of treatment plus 3 months posttreatment follow-up) in the combined studies (revised per Amendment 01)
- Change from baseline in ADAS-cog14, MMSE, and FAQ at 24 months in the combined studies
- Change from baseline in ADAS-cog14 Word List (immediate recall and delayed recall) at 24 months in the combined studies (revised per Amendment 01)

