Time to worsening of CDR scores by 24 months will be analyzed on the FAS using Cox regression model for treatment effect adjusting for randomization stratification factors. *ApoE4* status may be included in the model if appropriate. (revised per Amendment 06) Time to worsening of a CDR score is defined as time from randomization to worsening of the CDR score (ie, the first worsening in 2 consecutive scheduled visits). For subjects whose CDR scores have not worsened by the end of the Treatment Period of the Core Study, the time to worsening of the CDR score will be censored at the date of last CDR assessment for these subjects.

Time to conversion to dementia for subjects who were not clinically staged as dementia at Baseline based on clinical diagnosis will be analyzed on the FAS using Cox regression model for treatment effect adjusting for randomization stratification factors. *ApoE4* status may be included in the model if appropriate. (revised per Amendment 06) Proportion of subjects with

dementia diagnosis at 24 months will be estimated using Kaplan—Meier method based on time to conversion to dementia based on clinical diagnosis. Time to conversion to dementia for subjects who were not clinically staged as dementia at Baseline based on clinical diagnosis is defined as time from randomization to conversion to dementia based on clinical diagnosis. For subjects without clinical dementia by the end of study, the time to conversion to dementia based on clinical diagnosis will be censored at the date of last dementia diagnosis.

The other continuous secondary efficacy endpoints as defined above will be analyzed using the same MMRM model as the primary efficacy analysis to compare elenbecestat 50 mg per day versus placebo on the FAS, using baseline value corresponding to the response variable in the model.

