9.7.1.6.3 EXPLORATORY EFFICACY ANALYSES

Time to change of concomitant AD treatment will be analyzed similarly to that for time to conversion to dementia based on clinical diagnosis. Time to change of concomitant AD treatment is defined as time from randomization to the first dose increase and/or initiation of treatment with AChEI or memantine after randomization. For subjects without any change of concomitant AD treatment by the end of study, the time to change of concomitant AD treatment will be censored at the date of last assessment of concomitant medication.

The proportion of subjects with any change of concomitant AD treatment at 24 months will be analyzed similarly to that for proportion of subjects with dementia diagnosis at 24 months.

The rate of change over time (mean slope) based on change from baseline in the NPI-10 item will be analyzed in a manner similar to that used for the rate of change over time (mean slope) based on change from baseline in the CDR-SB.

The analysis of the following exploratory efficacy endpoints will be performed to compare elenbecestat versus placebo using the appropriate prespecified statistical methods including MMRM model, analysis of covariance model (ANCOVA), etc. For each exploratory efficacy endpoint, the treatment effect for elenbecestat 50 mg per day versus placebo will be tested at a significance level of 2-sided alpha = 0.05.

- Change from baseline in NPI-10 item at 24 months

- Change from baseline in EQ-5D (subject self-reported, study partner self-reported, and subject measured by proxy) and QOL-AD (subject and study partner) at 24 months
- Change from baseline in Zarit's Burden Interview at 24 months

Additional analyses may be performed as needed.

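### Time to conversion to dementia is defined to 24 months, but its analysis rule has no 24-month cut, so the Cox model takes in conversions first staged at Month 27, off drug

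*Protocol*

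**What the plan says.** Among the other secondary endpoints, Protocol 9.7.1.1.2 lists "Time to conversion to dementia by 24 months for subjects who were not clinically staged as dementia at Baseline". The synopsis has the same wording.

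Section 9.7.1.6.2 analyses it by Cox regression on the Full Analysis Set, adjusted for the stratification factors. The event time "is defined as time from randomization to conversion to dementia based on clinical diagnosis", with no upper limit. The censoring sentence is: "For subjects without clinical dementia by the end of study, the time to conversion to dementia based on clinical diagnosis will be censored", and the censoring date is that of the last dementia diagnosis. The same section also gives a Kaplan-Meier proportion with dementia, read at 24 months.

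On timing, section 9.1.4 states: "The end of the Core Study will be the date of the last study visit (Visit 15) for the last subject". Section 9.1.2.2 puts Visit 15 at 12 weeks after the last dose. Table 5 places it at Day 813, nominal Month 27, and schedules disease staging at Visits 6 to 13, at early discontinuation and at Visit 15. The Visit 15 staging carries no footnote restricting it to subjects entering the Extension Phase.

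Two neighbouring rules matter. Time to CDR worsening, also defined to 24 months, is worded differently: "For subjects whose CDR scores have not worsened by the end of the Treatment Period of the Core Study". The exploratory time to change of AD treatment is defined to 24 months in 9.7.1.1.4, but 9.7.1.6.3 reads "For subjects without any change of concomitant AD treatment by the end of study".

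**The concern.** The endpoint and its analysis rule describe different follow-up periods. A completer who is not demented at Month 24 and is first staged as demented at Visit 15 is outside the endpoint as defined, but is an event under the analysis rule. The Cox model is the stated analysis of the treatment effect, and its hazard ratio uses every counted event.

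The protocol elsewhere keeps the two periods apart. CDR worsening is judged to the end of treatment, and CDR-SB at 27 months is a separate secondary endpoint. At stake is whether the reported hazard ratio estimates the stated endpoint. If the cut is left open, it could also be chosen after the data are seen.

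**Working it through.** **1. Timeline (Table 5).** Visit 13 is Day 729 (Month 24) and Visit 15 is Day 813. The gap is 813 − 729 = 84 days, or 12 weeks. Staging at Visits 6 to 13 gives eight occasions up to Month 24, and Visit 15 adds one after it.

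**2. The texts side by side.**

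| Endpoint | Horizon in definition | Status judged at | Censoring date |
|---|---|---|---|
| Conversion to dementia | 24 months | end of study | last dementia staging |
| CDR worsening | 24 months | end of Treatment Period | last CDR assessment |
| Change of AD treatment | 24 months | end of study | last medication assessment |

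For a non-converting completer, the last staging is Visit 15. The first and third rows conflict with their own definitions. The second limits event status correctly but does not cut the censoring date, and Table 5 schedules the CDR at Visits 14 and 15.

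**3. Plan figures.** None exist for this endpoint. The only sizing is for CDR-SB, and it reproduces: 2 × (1.960 + 1.282)² × 2.05² / 0.365² gives 663 per arm, and 663/0.70 gives 948 against the stated 950. It has no bearing here.

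**4. Size, under assumptions.** Assume a constant hazard, 24-month placebo conversion of 20–50%, an on-drug hazard ratio of 0.75 and an event-weighted average log hazard ratio. Take 30% placebo conversion, per subject in each arm, without dropout:

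- Monthly hazard: −ln(0.70)/24 = 0.01486.
- Events to Month 24: 0.3000 + (1 − 0.70^0.75) = 0.3000 + 0.2347 = 0.5347.
- Chance of conversion in the next 3 months at the placebo hazard: 1 − exp(−3 × 0.01486) = 0.0436.

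*Effect lost off drug.* Extra events are 0.70 × 0.0436 + 0.7653 × 0.0436 = 0.0305 + 0.0334 = 0.0639. Their share is f = 0.0639/(0.5347 + 0.0639) = 0.107. The hazard ratio is exp[(1 − 0.107) × ln 0.75] = 0.773. The test statistic is multiplied by √(1 − f) = 0.945. Starting from 80% power, 0.945 × 2.802 − 1.960 = 0.688, so power is about 75%.

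*Effect fully kept.* Extra events are 0.0305 + 0.0252 = 0.0557, so f = 0.0557/0.5904 = 0.094. The hazard ratio stays 0.750. The multiplier is 1/√(1 − 0.094) = 1.051, and 1.051 × 2.802 − 1.960 = 0.984, so power is about 84%.

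Repeating this for 20–50% conversion, without dropout and with 30% dropout (the rate in 9.7.2, taken as a constant loss rate):

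| Off-drug effect | Share after Month 24, no dropout | Share, 30% dropout | Hazard ratio | 80% power becomes |
|---|---|---|---|---|
| None | 9–11% | 7–9% | 0.766–0.775 | 75–77% |
| Half the log ratio | 8–11% | 7–9% | about 0.76 | about 80% |
| Full | 8–10% | 6.5–8% | 0.750 | 83–84% |

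**The case against.** **Read together, the sections already exclude Month 27.** Section 9.7.1.6.2 analyses an endpoint that 9.7.1.1.2 limits to 24 months, and no sentence says that a Visit 15 conversion counts. An analysis plan could settle the window. That is a fair account of the likely intent. But the analysis section defines the event time afresh without a limit and names a later point for judging status, while the adjacent rule names the end of treatment. The two statements still conflict within the protocol.

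**The horizon could be reconciled the other way.** The objective in 8.2 has no 24-month limit, so deleting it from the endpoint would also remove the conflict. This stands as an alternative. The Kaplan-Meier reading at 24 months, the CDR-worsening rule and the separate Month-27 CDR-SB endpoint all favour keeping 24 months.

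**Stronger readings that the documents do not support.**

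- A reader might infer a definite loss of power. That needs the effect to vanish once dosing stops. The Amendment 01 rationale for adding CDR-SB at 27 months is to assess disease modification after treatment, which points the other way, and with a persisting effect power rises.
- A reader might take the rule to censor at the end of study. It judges status then and censors at the last staging.
- A reader might suppose that Extension Phase conversions enter, since Appendix 5 gives a later end of study. The rule belongs to the Core Study methods, and the Extension Phase has its own conversion endpoint.
- A reader might see a clean split between on-drug and off-drug time. Early discontinuers can be staged off drug before Month 24, and those conversions belong in the endpoint under the intent-to-treat approach stated for the primary analysis.

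**Conclusion.** The conflict holds. As written, the Cox hazard ratio for conversion to dementia includes events outside the endpoint's 24-month horizon. They are roughly 8–11% of events under a constant hazard without dropout, and somewhat fewer with dropout. Whether this changes the estimate depends on what happens after the last dose, which the documents do not quantify: about 0.77 instead of 0.75 if the effect is lost, no change if it persists. Power moves in opposite directions in the two cases. Conversion rates, the 0.75 ratio and the 80% starting power are all assumptions.

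The severity is minor. The endpoint lies outside the testing hierarchy, and its 24-month Kaplan-Meier proportion, the primary analysis and the key secondary tests are untouched. The change-of-treatment endpoint has the same mismatch and is exploratory; Table 5 records concomitant medication at Visit 15.

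**What to change.** In 9.7.1.6.2 and the synopsis, state that conversions count if staged on or before the Month-24 assessment (Visit 13 with its window, so up to Day 729 + 10 = Day 739 from the start of treatment), and that non-converters are censored at their last staging on or before that point. Write the censoring cut out in full. Borrowing the CDR-worsening wording would not do, because it limits event status only. Say that off-drug conversions in early discontinuers still count when they fall before the cut.

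Apply the same 24-month cut to time to change of AD treatment in 9.7.1.6.3 and the synopsis.

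The cost is one sentence per endpoint and the removal of the Month-27 events from the Cox model. No visit, sample size or test in the hierarchy changes. It should be settled before unblinding.

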9.7.1.6.3 EXPLORATORY EFFICACY ANALYSES

Time to change of concomitant AD treatment will be analyzed similarly to that for time to conversion to dementia based on clinical diagnosis. Time to change of concomitant AD treatment is defined as time from randomization to the first dose increase and/or initiation of treatment with AChEI or memantine after randomization. For subjects without any change of concomitant AD treatment by the end of study, the time to change of concomitant AD treatment will be censored at the date of last assessment of concomitant medication.

The proportion of subjects with any change of concomitant AD treatment at 24 months will be analyzed similarly to that for proportion of subjects with dementia diagnosis at 24 months.

The rate of change over time (mean slope) based on change from baseline in the NPI-10 item will be analyzed in a manner similar to that used for the rate of change over time (mean slope) based on change from baseline in the CDR-SB.

The analysis of the following exploratory efficacy endpoints will be performed to compare elenbecestat versus placebo using the appropriate prespecified statistical methods including MMRM model, analysis of covariance model (ANCOVA), etc. For each exploratory efficacy endpoint, the treatment effect for elenbecestat 50 mg per day versus placebo will be tested at a significance level of 2-sided alpha = 0.05.

- Change from baseline in NPI-10 item at 24 months

- Change from baseline in EQ-5D (subject self-reported, study partner self-reported, and subject measured by proxy) and QOL-AD (subject and study partner) at 24 months
- Change from baseline in Zarit's Burden Interview at 24 months

Additional analyses may be performed as needed.

9.7.1.7 Pharmacokinetic, Pharmacodynamic, Pharmacogenomic, and Other Biomarker Analyses

9.7.1.7.1 PHARMACOKINETIC ANALYSES

Safety Analysis sets will be used for individual elenbecestat plasma and CSF concentration listings. The PK Analysis Set will be used for the summaries of elenbecestat plasma and CSF concentrations.

A population PK approach will be used to characterize the PK of elenbecestat. The effect of covariates (ie, demographics) on elenbecestat PK will be evaluated. The PK model will be parameterized for clearance (CL) and volumes of distribution. Derived exposure parameters such as AUC will be calculated from the model using the individual posterior estimate of CL and dosing history.

9.7.1.7.2 PHARMACOKINETIC-PHARMACODYNAMIC

The PK/PD relationship between CSF biomarker levels and plasma PK parameters or CSF concentrations of elenbecestat will be explored graphically and any emergent relationship will be explored through population PK/PD modeling. These PK parameters include maximum observed concentration (C_{max}), and $AUC_{(0-24)}$ derived from the population PK model. The PK/PD relationship between plasma PK parameters and CSF concentrations of elenbecestat with other biomarkers may also be explored using similar methods.

Additionally, the relationship between various PK parameters (eg, C_{max}) or CSF concentrations of elenbecestat and CDR-SB at 24 months, and the relationship between various PK exposure parameters or CSF concentrations of elenbecestat and the change from Baseline for 24 months in ADAS-cog14, and the MMSE, will be explored graphically. Any emergent relationships will be explored through population PK/PD modeling. The relationship between exposure to elenbecestat and most frequent AEs will also be explored.

9.7.1.7.3 PHARMACODYNAMIC, PHARMACOGENOMIC, AND OTHER BIOMARKER ANALYSES

The analysis of the biomarker endpoints defined as below will be performed to compare elenbecestat versus placebo using the appropriate prespecified statistical methods including MMRM model, ANCOVA, or non-parametric methods if the data is not normally distributed, etc. These analyses will be conducted without adjustment for multiplicity or sequential testing. For each endpoint, the treatment effect for elenbecestat 50 mg per day versus placebo will be tested at a significance level of 2-sided alpha = 0.05. (revised per Amendment 05)

- Change from baseline in tau PET signal at 24 months (revised per Amendment 05)

- Change from baseline in CSF biomarkers t-tau and p-tau at 24 months
- Change from baseline in CSF amyloid biomarkers $A\beta(1-42)$, and $A\beta(1-x)$ at 24 months (revised per Amendment 04)
- Change from baseline in total hippocampal volume at 12 and 24 months using vMRI
- Change from baseline in fMRI parameters as appropriate (revised per Amendment 06)
- Change from baseline in plasma amyloid biomarker (eg, $A\beta(1-x)$) at all assessments (revised per Amendment 06)
- Change from baseline in potential plasma and CSF biomarkers of AD (eg, NFL, VILIP1, YKL-40, and Ng) (revised per Amendment 06)

The relationship between exposure (in CSF, plasma) of elenbecestat with potential biomarkers of Alzheimer's disease as deemed appropriate will be evaluated using appropriate statistical model with the continuous changes in biomarker at 24 months as response variables and exposure variables (in CSF, plasma) of elenbecestat as independent variables.

9.7.1.8 Safety Analyses

Evaluations of safety will be performed on the Safety Analysis Set. The incidence of AEs, out-of-normal-range laboratory safety test variables, abnormal ECG findings, and out-of-range vital signs, suicidality, events of possible signals of drug abuse potential, results of the sleep questionnaire, along with change from baseline in laboratory safety test variables, ECGs, and vital sign measurements will be summarized by treatment group. (revised per Amendments 01 and 06)

9.7.1.8.1 EXTENT OF EXPOSURE

The Duration of exposure to study drug will be summarized as cumulative extent of exposure in categories with 3-month increment. The cumulative number and percent of subjects in each applicable exposure category will be presented by treatment group. Duration of exposure will be summarized using descriptive statistics as well as by 3-month duration categories using counts. The number and percent of subjects within each duration category will be presented by treatment group. Overall exposure (number of subject-months) is defined as summation over all subjects' exposure durations and will be summarized by treatment group.

9.7.1.8.2 ADVERSE EVENTS

The AE verbatim descriptions (investigator terms from the eCRF) will be classified into standardized medical terminology using the Medical Dictionary for Regulatory Activities (MedDRA). AEs will be coded to the MedDRA (Version 19.0 or higher) lower level term closest to the verbatim term. The linked MedDRA PT and primary system organ class (SOC) are also captured in the database.

A TEAE is defined as:

- An AE that emerges on or after start of study treatment, having been absent at pretreatment (Baseline) or
- Reemerges on or after start of study treatment, having been present at pretreatment (Baseline) but stopped before treatment, or
- Worsens in severity on or after start of study treatment relative to the pretreatment state, when the AE is continuous. (revised per Amendment 04)

Only those AEs that are treatment-emergent will be included in summary tables. All AEs, treatment-emergent or otherwise, will be presented in subject data listings.

The TEAEs will be summarized by treatment group on the Safety Analysis Set. The incidence of TEAEs will be reported as the number (percentage) of subjects with TEAEs by SOC and PT. A subject will be counted only once within an SOC and PT, even if the subject experienced more than 1 TEAE within a specific SOC and PT. The number (percentage) of subjects with TEAEs will also be summarized by maximum severity (mild, moderate, or severe). The number (percentage) of subjects with TEAEs will also be summarized by relationship to study drug (Yes [related] and No [not related]).

The number (percentage) of subjects with treatment-related TEAEs will be summarized by SOC and PT. Treatment-related TEAEs include those events considered by the investigator to be related to study drug. The number (percentage) of subjects with treatment-related TEAEs will also be summarized by maximum severity (mild, moderate, or severe).

AEs will be summarized by the following subgroups: region, prior treatment with AChEIs or memantine (no or yes), and clinical subpopulation (MCI due to AD or the early stages of AD). (revised per Amendment 01)

The number (percentage) of subjects with TEAEs leading to death will be summarized by MedDRA SOC and PT for each treatment group. A subject data listing of all AEs leading to death will be provided. The number (percentage) of subjects with treatment-emergent SAEs will be summarized by MedDRA SOC and PT for each treatment group. A subject data listing of all SAEs will be provided. The number (percentage) of subjects with TEAEs leading to discontinuation from study drug will be summarized by MedDRA SOC and PT for each treatment group. A subject data listing of all AEs leading to discontinuation from study drug will be provided.

